9.5 Baseline Values

Baseline values are from screening/baseline visit for all measures, except C-SSRS. For C-SSRS, pre-enrollment scores will be used as a measure of 'lifetime' suicidal ideation and behavior, and preparatory session 2 (visit 2) prior to drug administration will used as 'baseline.' If a subject was not administered the C-SSRS at preparatory session 2 (visit 3), then 'baseline' scores will be visit 4 pre-drug C-SSRS observation.

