5.2.3 Experimental Sessions (Visit 4 and 8)

Subjects in Stage 1 will receive two double-blind experimental sessions of MDMA-assisted psychotherapy scheduled approximately 3-5 weeks apart, and subjects in the open label leadin and open label Stage 2 will receive two experimental sessions with the full dose of MDMA. Procedures for MDMA-assisted psychotherapy will remain the same across all sessions, and all procedures except the drug received will be the same.

- a. At least 24 hours prior to the first experimental session the subject will be randomized. The therapist team conducting the session will obtain the container assignment using a web-based randomization program prior to the session.
- b. On the day of the experimental session, the subject will arrive approximately 1-1.5 hours prior to drug administration.
- c. Confirm continuing eligibility by reviewing inclusion/exclusion criteria.
- d. Perform a urine drug screen. A positive drug screen will be reviewed by the investigator and may be cause for delaying drug administration to a later time, rescheduling the session to a later date, or withdrawing the subject from the study.
- e. If a woman is of childbearing potential, perform a urine pregnancy test. A positive pregnancy screen is cause for withdrawal from the protocol.
- f. If the subject continues to meet criteria and the subject reports that he/she followed appropriate rules and restrictions, the session will proceed.
- g. Review procedures for the experimental session with the subject.
- h. Record the entire session to video and audio. Subjects may receive a copy of audio or video recordings of their experimental sessions upon request.
- i. The session will last for approximately eight hours or longer, followed by an overnight stay at the study site.
- j. The subject will complete the C-SSRS approximately one hour to a half hour prior to drug administration.

Table 4. Schedule of procedures and measures for experimental sessions.

Approximate Time	Procedure or Action
9:00	Urine drug screen and pregnancy test. Subject acclimated to
0.45	environment, C-SSRS
9:45	Baseline BP, Pulse, Subjective Units of Distress Rating (SUD)
9:55	2 nd Baseline BP, Pulse, Body Temperature (BT), SUD
10:00	MDMA Administration, begin recording to audio and video
10:30	BP, Pulse
11:00	BP, Pulse, SUD, BT
11:30	BP, Pulse; Can administer optional supplemental dose
12:00	BP, Pulse, BT
12:30	BP, Pulse, SUD
13:00	BP, Pulse
13:30	BP, Pulse, BT
14:00	BP, Pulse, SUD

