Every hour, and as	BP, Pulse
needed	
Every 60-90 minutes	SUD, BT
Approximately 6	C-SSRS, General Wellbeing
hours after drug	
administration	

- k. Before drug administration, discuss and review the subject's goals, intentions and concerns and some of the commonly experienced effects of MDMA.
- 1. Instruct the subject not to use caffeine or nicotine 1 hour before or 3 hours after the dose of drug.
- m. Subject body temperature will be measured 15 and 5 minutes prior to initial dose administration and approximately every hour after that. The therapists may make more frequent measurements if body temperature exceeds more than 1°C above baseline.
- n. Subjects will complete the SUD 15 and 5 minutes prior to initial dose administration. Subjects will complete the SUD every 60 to 90 minutes, until the session is over, allowing a window of up to 30 minutes to fit into the psychotherapy process where a natural break occurs. If necessary, the therapists can make a greater number of measurements as their clinical judgment dictates.
- o. Measure blood pressure and pulse 15 and 5 minutes prior the experimental session, and once every half-hour throughout the experimental session if the established thresholds for normal blood pressure and pulse have not been exceeded for the duration of the experimental session. More frequent measures will be taken if the established thresholds of 160 systolic, 110 diastolic or pulse 110 are exceeded. Measurements should be taken every 5 minutes until the values fall below these levels or until they have been decreasing for 15 minutes or have stabilized at a level judged by the investigator to be safe. The therapists may also make more frequent measurements if a subject exhibits symptoms indicative of hypertension.
- p. At approximately 10:00 in the morning, subjects will receive the initial dose of drug along with a glass of water.
- q. The subject will sit or recline on comfortable furnishings. Eyeshades and a program of music will be provided if the subject wishes to use them. Subjects will listen to a program of music designed to support their experience by initially aiding relaxation and later evoking and supporting deep emotions and the emergence of unconscious material [77-79]. Subjects may speak to the therapists whenever they wish, who will provide guidance and support as needed.

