Descriptive statistics will be calculated for all measurements overall and within the two dose conditions. Distributional characteristics will be examined for outliers and extreme values and, if either is evident, nonparametric statistics will be utilized in the analysis. Effect size of Active Placebo and Full Dose MDMA for all outcome measures for Stage 1, Stage 2, and 12 months after the final experimental session will be estimated using Cohen's techniques.

There is no expectation that conditions will differ in composition by gender, race or ethnicity, duration of PTSD diagnosis or presence versus absence of other permitted psychiatric disorders, as depression. However, owing to small sample size, such variations may arise by chance.

The therapists will record average baseline and post-drug peak blood pressure, heart rate and body temperature for participants during experimental sessions. The therapists will also record spontaneously reported reactions and AEs as described in section 8.5. Descriptive statistics will be computed for vital signs and subjective distress during each experimental or open-label session. The sponsor will informally or formally compare peak blood pressure, heart rate and body temperature for participants after sessions with Active Placebo or Full Dose MDMA. Frequency tables will be produced on prevalence of spontaneously reported reactions and AEs.

An interim analysis may be completed when all participants have completed the main study, including stage 1 and Stage 2, but not all participants have completed the 12-month follow-up evaluation. Additionally, an interim analysis may be performed after all participants have completed Stage 1 but not necessarily before all eligible participants complete Stage 2. This analysis will address both safety and efficacy of the treatment.

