4.3 Safety Objectives

The safety objectives of the study are to monitor and assure safety of subjects during and after the experimental sessions by assessing physiological effects, psychological distress, adverse events, spontaneously reported reactions and suicidality.

- Suicidality will be assessed with the Columbia Suicide Severity Rating Scale (C-SSRS) during visits prior to experimental sessions, twice during experimental sessions, and several times after each experimental session, with comparisons made between subjects in each condition.
- Subjective Units of Distress (SUD) scores and vital signs including blood pressure, heart rate and temperature will be measured during each experimental session, and results will be compared between groups.
- Serious adverse events, adverse events and spontaneously reported adverse events ("reactions") will be collected during the study according to Section 8.5.

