Vital signs (heart rate, body temperature, systolic and diastolic blood pressure) will be summarized using descriptive statistics at baseline and at each post-baseline time point. Occurrences of systolic and diastolic blood pressure, heart rate, and body temperature readings above the pre-determined cutoff will be displayed with numbers and percentages by timepoint.

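### SAP 9.5 sets baseline at screening for every measure except C-SSRS, which cannot be applied to SUD and, for vital signs, conflicts with the protocol's same-session pre-dose baseline

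*SAP*

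**What the plan says.** SAP 9.5 gives one general rule: "Baseline values are from screening/baseline visit for all measures, except C-SSRS". For C-SSRS it names the second preparatory session, and falls back on the pre-drug observation at visit 4. SUD and vital signs are both safety measures under SAP 8.2, so the general rule covers them.

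SAP 9.9.4 says that vital signs "will be summarized using descriptive statistics at baseline and at each post-baseline time point". It also plans counts of readings above a cutoff that it does not state, and a descriptive summary of SUD by Stage 1 group and time period. It does not redefine baseline for either. The safety objective in SAP 4.3 says that "Subjective Units of Distress (SUD) scores and vital signs including blood pressure, heart rate and temperature will be measured during each experimental session", with results to be compared between groups.

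The protocol works from the session. Table 4 in Protocol 5.2.3 schedules two sets of readings, at 9:45 and 9:55, before dosing at 10:00, and labels both as baseline; the second covers "Baseline BP, Pulse, Body Temperature (BT), SUD". Item n of the same section adds: "Subjects will complete the SUD 15 and 5 minutes prior to initial dose administration". Protocol 12.0 states: "The therapists will record average baseline and post-drug peak blood pressure, heart rate and body temperature for participants during experimental sessions".

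**The concern.** The general rule in SAP 9.5 does not fit measures that are taken around dosing. It points SUD to a visit at which SUD is not collected. It points vital signs to an examination done weeks earlier in another setting, although the protocol collects readings minutes before the dose and calls them baseline.

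What is at stake is how a reported safety summary reads. The acute cardiovascular, temperature and distress response in the sessions is a stated safety objective. A reader of the vital-sign table would take the baseline row as the pre-drug state on the day. A screening value in that row is not that. The readings that do show the pre-drug state would sit among the post-baseline time points, and two programmers working from the same SAP could produce different tables.

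**Working it through.** No power or sample-size figure is involved. The check is whether the rule can be applied to the schedule, how old the screening value would be, how many sessions are touched, and which planned outputs use a baseline.

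**1. Values available at each place**

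| Measure | At screening | Pre-dose, each session |
|---|---|---|
| SUD | None. Marked only at V4 and V8 (Time and Events, Stage 1) and V14 and V18 (Stage 2); absent from Protocol 5.2.1 | 2 (Table 4; item n) |
| Blood pressure, pulse | Physical examination, Protocol 5.2.1 | 2 (Table 4; item o) |
| Body temperature | Physical examination, Protocol 5.2.1 | 1 in Table 4 (9:55), but 2 in item m |

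So SAP 9.5 yields no SUD baseline for any subject, and for vital signs it selects the physical-examination reading.

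**2. Age of the screening reading**

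Inputs: screening up to one month before V1 (Protocol 5.2.1); V4 at 3-5 weeks after V1 and V8 at 3-5 weeks after V4 (Time and Events table). One month is taken as 30 days. The lower end assumes that screening is completed immediately before V1.

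- To session 1 (V4): (0 to 30) + (21 to 35) = 21 to 65 days, or 3 to 9.3 weeks.
- To session 2 (V8): (21 to 65) + (21 to 35) = 42 to 100 days, or 6 to 14.3 weeks.

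The gap is longer if washout delays V4, and longer again for Stage 2 sessions. Protocol 5.2.2 starts the taper of psychiatric medication on enrollment at V1. In a subject who tapers, the screening reading may therefore be on medication and the session readings off it.

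**3. Sessions and readings**

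- Randomized Stage 1: 8 subjects x 2 = 16 sessions, and 16 x 2 = 32 pre-dose blood pressure and pulse readings.
- All stages, if all three comparator subjects cross over and before replacements: (8 + 2) x 2 + 3 x 2 = 26 sessions, and 26 x 2 = 52 readings.

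Under the literal rule all of these fall after baseline. With a session-specific baseline none does.

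**4. Planned outputs that use a baseline**

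- Vital signs: the baseline row in SAP 9.9.4 would hold screening values. The paragraph specifies no change from baseline and no test.
- SUD: summarized by time period only, with no change score and no test.
- CAPS-4 and the other outcome scales: collected at screening, so the rule fits them at Stage 1.

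**The case against.** The best defence is that this is mainly a labelling matter. The pre-dose readings are collected and can be shown at their own time points whatever row is called baseline. An analyst who knew Table 4 might use them without being told. The Time and Events table gives session monitoring of blood pressure, pulse and temperature its own row, marked only at sessions, so it is an inference that the physical examination would supply the vital-sign baseline. SAP 5.0 also names the protocol as the authority.

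Part of this stands: the pre-dose data are not lost, and the harm is to the clarity of a descriptive table. The rest does not remove the conflict. If the physical examination is not the vital-sign baseline, SAP 9.5 gives vital signs no baseline at all, which is the same defect as for SUD. The sentence in SAP 5.0 sits in a design overview, while SAP 9.0 says that the SAP amends the protocol's analysis plan. SAP 9.0 gives small groups and parametric tests as its reason, so neither sentence clearly settles which baseline applies. SAP 9.5 itself provides a pre-drug fallback for C-SSRS and nothing similar for the session measures.

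A reader might infer more than the documents support:

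- **That change in SUD cannot be computed.** It can be, from the readings 15 and 5 minutes before dosing. The SAP simply does not call them baseline, and plans no SUD change score.
- **That anticipation or day-to-day variation will be counted as drug effect.** That needs a change-from-baseline analysis, and SAP 9.9.4 specifies none.
- **That counts above the cutoff will be wrong.** The blood pressure and pulse thresholds in Protocol 5.1.2 are absolute, so baseline would not affect them. The temperature rule relative to baseline is a site action during the session, and the SAP does not say that its cutoff is relative. The documents give no figure for the difference between screening and pre-dose temperature, so no error can be sized.
- **That general well-being needs a baseline too.** It is first scheduled at V1, but SAP 9.9.4 plans no analysis of it.

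**Conclusion.** The point holds, at modest size. SAP 9.5 states a rule that cannot be applied to SUD and that, for blood pressure, pulse and temperature, contradicts the baseline used in Protocol Table 4 and Protocol 12.0. Read literally, it puts the wrong values in one row of a reported safety table and misclassifies the pre-dose readings.

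The consequence stays within descriptive safety summaries in a pilot whose significance testing is exploratory (SAP 7.0). The primary CAPS-4 analysis does not depend on it. The conclusion rests on reading SAP 9.5 as written; the intervals rest on the scheduled windows, and the session counts on full crossover without replacements. It is worth correcting because the summary bears on a stated safety objective and the remedy is small.

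**What to change.** Amend SAP 9.5 along these lines: for blood pressure, heart rate, body temperature and SUD, baseline is defined separately for each experimental session (V4, V8, V14 and V18) as the mean of the available pre-dose readings at that session; these readings are not post-baseline time points; screening vital signs are reported separately as screening values.

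The mean of available readings also covers sessions with one pre-dose temperature and sessions with two. Table 4 and item m of Protocol 5.2.3 differ on that number and should be reconciled.

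The cost is one SAP paragraph. All the readings are already scheduled, and no assessment, visit or clinical rule changes. SAP 2.0 has the plan finalized before any unblinded, inferential or descriptive analysis, and the amendment belongs before that point.

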9.6 Subject Disposition and Dosing Summary

All subjects enrolled in the study (i.e., who sign informed consent and complete inclusion/exclusion criteria) will be included in the summary of subject disposition and accountability. No inferential statistical tests will be performed. The tabulation of number of subjects in each treatment group and overall will be displayed for all subjects in the Safety Population, in the mITT Population, and in the PP Population. The number and percent of subjects who completed or discontinued the study will be displayed for each treatment group and overall together with reasons for early termination, where the percent is with respect to the total number of randomized subjects in that treatment group. The timepoint of doses and total MDMA (mg) administered will be summarized by treatment group for the Safety, mITT and PP Populations.

9.7 Demographics and Baseline Characteristics

Subject demographic data and baseline characteristics will be summarized descriptively by treatment group and overall. The demographic data and baseline characteristics will be summarized for the mITT and Crossover Populations.

9.8 **Prior and Concomitant Medications**

The number and percent of subjects who took medications prior to and after signing informed consent will be summarized descriptively for each treatment group. Concomitant medications will be summarized similarly. Prior and concomitant medications will be summarized for the Safety Population. Psychiatric medications will be coded to common drug classes and terms.

9.9 Effect Analyses

For all primary, secondary and exploratory endpoints descriptive statistics (n, mean, standard deviation, median, range, effect size (for measures of interest), or counts and percentages where appropriate) will be provided by treatment group.

Effect size (Cohen's *d*) for each treatment group will be determined by employing an independent-groups pretest-posttest design (IGPP), where the mean difference in the pretest-posttest is divided by the standard deviation of raw scores, and then the control group effect size is subtracted from the experimental group effect size [1].

$$\frac{d_{IGPP} = \frac{X_{postT} - X_{PreT}}{S_{T}} \qquad \frac{X_{postC} - X_{PreC}}{S_{C}}$$

X = treatment means

 S_T and S_C = pooled SD of pre- and post-test by group

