12.1 Statistical Power

This is a pilot study, and as such, power analysis was not conducted for the study. The study is underpowered for detection of differences of a small or moderate effect size, and it may detect differences if the effect size is large.

Analyses of MAPS' completed US study of MDMA-assisted psychotherapy in 20 people with PTSD found an effect size of 1.24 for treatment efficacy, as represented by changes in CAPS score [2]. The estimated effect size for this study may be lower as a result of comparing the full dose of MDMA with a low dose of MDMA instead of with inactive placebo, small sample size and unequal distribution of conditions. The sponsor intends to pool data across studies or perform meta-analyses of CAPS scores across all pilot studies.

The sponsor used Java applications created by Lenth and posted on the website listed below to calculate estimated statistical power for this study, assuming an effect size of 0.8 for the impact of two sessions of MDMA-assisted psychotherapy on symptoms of PTSD and depression [100], reducing the effect size to account for the hypothesized effects of using an active placebo. The software calculated an estimated power of 0.15, indicating an underpowered study. Had we used the higher effect size of 1.1, power analysis still indicates that this study is underpowered, with an estimated effect size of 0.25. Without previous data concerning the effects of MDMA-assisted psychotherapy upon sleep quality, no power estimates have been made for differences in sleep quality between full dose and active placebo participants.

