9.0 Analyses

In general, nominal variables will be described in terms of frequencies and percentages and analyzed using chi square analysis. Although the protocol plan specifies parametric t-tests and ANOVAs, the small group sizes (n=3 and n=5) make it a challenge to statistically assess the effectiveness of the treatment. Therefore, this statistical analysis plan acts to amend the data analysis plan in the protocol.

Clinical data will be presented in tabular format. Data not subject to analysis according to this plan will not appear in any tables or graphs, but will be included in the data listings. Analyses will be carried out with SAS Version 9.3 or higher. Selected results may be presented graphically using standard graphical software.

Post-hoc exploratory analyses not identified in this SAP may be performed to further examine the study data. These analyses will be clearly identified as such in the final clinical study report.

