9.9.1 Primary Effect Analyses

Clinician Administered PTSD Scale-4 (CAPS-4)

The primary effect evaluation is the change from baseline to the end of stage 1 outcome timepoint (visit 12) in the CAPS-4 Global Severity score of PTSD (difference score).

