9.9.2 Secondary Effect Analyses

The secondary effect analyses will be made comparing change from baseline (Baseline) to the end of stage 1 outcome timepoint (visit 12) of all the secondary measures except the PDS, following the same methodology used for the primary endpoint.

PTSD Diagnostic Scale (PDS) total scores will be analyzed in the same manner as the CAPS-4 global scale primary analysis.

Global Assessment of Functioning (GAF) total score will be analyzed in the same manner as the CAPS-4 global scale primary analysis.

Beck Depression Inventory-II (BDI-II) total score will be analyzed in the same manner as the CAPS-4 global scale primary analysis.

Pittsburgh Sleep Quality Index (PSQI) global scores will be analyzed in the same manner as the CAPS-4 global scale primary analysis.

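### SAP 9.9 divides each arm's CAPS change by that arm's own SD (n=5 and n=3); one common SD would give a steadier effect size that cannot contradict the raw difference

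*SAP*

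**What the plan says.** SAP 9.9 defines the effect size as an independent-groups pretest-posttest statistic. In each arm the mean change "is divided by the standard deviation of raw scores", and then "the control group effect size is subtracted from the experimental group effect size". The key to the formula says that S_T and S_C are the "pooled SD of pre- and post-test by group", so each arm has its own divisor. SAP 9.9.1 names the CAPS-4 change from baseline to visit 12 as the primary evaluation, with no test, interval or raw between-arm contrast. SAP 9.9.2 treats the secondary scales "following the same methodology used for the primary endpoint".

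SAP 9.0 notes that groups of 3 and 5 are a challenge for the protocol's t-tests and ANOVAs, and says that "this statistical analysis plan acts to amend the data analysis plan in the protocol". Its chi-square provision covers nominal variables only. SAP 9.9 also lists n, mean and SD by group. SAP 3.0 gives effect-size estimation as a purpose of the study, and SAP 7.0 says the estimates will serve power calculations for later studies.

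**The concern.** With separate divisors, d_IGPP = change_T/S_T - change_C/S_C. If the comparator does not change, the second term is near zero and its divisor matters little. If the comparator improves, sampling error in S_C, estimated from three people, scales a sizeable mean. The same happens with S_T in the other arm, and the two errors are independent. The result is noisier than the same raw difference over one common SD. It can also reverse sign against the raw difference, which one positive divisor cannot do.

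Comparator improvement is plausible here. Protocol 5.2.3 says that "all procedures except the drug received will be the same", so the 25 mg arm receives the same psychotherapy. Protocol 12.1 lowers the assumed effect, "reducing the effect size to account for the hypothesized effects of using an active placebo". At stake is the quality of the estimate the study exists to produce. If the tabulated means and d_IGPP disagree, the SAP does not say which figure prevails.

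**Working it through.** **Design inputs.** Group sizes are 5 and 3 (SAP 6.0, 9.0); the planning effect is 0.8 and alpha 0.05 (protocol 12.1, 12.0). As a check on these, the protocol's power was reproduced. The noncentrality is 0.8/√(1/5+1/3) = 0.8/0.730 = 1.095. A two-sided t test with 6 df (critical value 2.447) then has power 0.153, against the stated 0.15. At 1.1 it is 0.247, against the stated 0.25 (which the protocol labels an effect size). These figures do not enter the argument below.

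**Sign reversal by arithmetic (invented numbers).** Full dose changes by -40 with SD 25: -40/25 = -1.6. Comparator changes by -30 with SD 15: -30/15 = -2.0. So d_IGPP = -1.6 - (-2.0) = +0.4, which favours the comparator, although full dose improved 10 points more.

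**How often, and how much noise.** The documents give no CAPS SD, pre/post correlation or comparator change. Assumed: normal scores with SD 1 at both visits in both arms; correlation 0.3, 0.5, 0.7; S as the root mean of the pre and post variances; true difference -0.8 SD; no small-sample correction on either side; 400,000 simulated trials per setting. The alternative is the raw difference in mean change divided by one SD pooled over both arms and both visits. The 0.44 setting is 1.24 - 0.8, the gap between the earlier study's effect and the planning value in protocol 12.1. The 1 and 2 SD settings have no source in the documents and serve as stress tests.

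| Comparator improvement (SD) | 0 | 0.44 | 1 | 2 |
|---|---|---|---|---|
| Sampling SD of d_IGPP / common-SD version | 1.22-1.28 | 1.31-1.49 | 1.51-1.97 | 2.06-3.10 |
| d_IGPP / version using baseline-only common SD | 1.07-1.15 | 1.15-1.34 | 1.33-1.76 | 1.81-2.77 |
| Sign of d_IGPP opposes raw difference | 6% | 10-12% | 16-20% | 25-31% |
| Same, with raw difference above 0.5 SD | 0.6% | 2-3% | 5-9% | 12-18% |
| d_IGPP favours comparator | 11-20% | 16-22% | 23-25% | 32-33% |

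Ranges run over the three correlations. The raw or common-SD difference favours the comparator in 8-18% of trials whatever the comparator does. This follows directly: its standard error is √(2(1-ρ)) × 0.730, so the probability is Φ(-0.8/0.864) = 0.177, Φ(-0.8/0.730) = 0.137 and Φ(-0.8/0.566) = 0.079 at ρ = 0.3, 0.5, 0.7.

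At comparator improvement 1 SD and ρ = 0.5, the central 95% of estimates runs from -3.3 to +2.2 for d_IGPP and from -2.7 to +0.7 for the common-SD version.

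**Unequal SDs.** If visit-12 SD is 1.5 times baseline in both arms, the ratio to the two-visit common SD is 1.23-1.30 with no comparator change and 1.43-1.75 at 1 SD. The ratio to the baseline-only version falls to 0.87-0.94 and 1.01-1.26. If only the comparator's visit-12 SD is 1.5 times the others (ρ = 0.5), the noise ratio is 1.18 and 1.47, but wrong-sign rates are about equal: 0.168 against 0.184 with no comparator change, and 0.179 against 0.183 at 1 SD.

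**The case against.** The strongest case is that this is a choice between recognised estimators. Own-arm divisors avoid assuming one variance across arms. If the true SDs differ, the two statistics target different quantities. With full-dose visit-12 SD 1.5, comparator change -1 and raw difference -0.8, the large-sample d_IGPP is -1.8/√((1+2.25)/2) + 1 = -0.41, so calling its sign wrong presumes interest in the raw difference. The planned meta-analysis (SAP 3.0) is a reason to keep one metric. That stands, and is why d_IGPP should still be shown.

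Second, means and SDs by group are already planned, so a reader could see a conflict and derive most of the alternative. That also stands, but leaves the choice of figure until after unblinding.

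Third, SAP 9.0 amends the protocol without expressly deleting its t-tests, and SAP 7.0 still allows exploratory testing. The exact claim is therefore that d_IGPP is the only between-arm statistic the SAP itself defines for these scores. The cited effect-size reference may also supply an interval, though that would not remove the noise or the sign problem.

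Fourth, part of the extra noise is small-sample inflation. Applying J(v) = 1 - 3/(4v-1) to both sides (J(8) = 0.903 and J(4) = 0.800 by arm; J(12) = 0.936 for the common SD) lowers the ratios to 1.09-1.15, 1.17-1.34, 1.35-1.77 and 1.84-2.75 across the four settings. Sign conflicts remain at 6% to 25%. This trims the noise by about 11% but does not remove the problem.

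Finally, many conflicts occur when the raw difference is small, and with no comparator change the problem is modest. Both are true.

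**Conclusion.** The point holds as a minor, low-cost improvement. It does not threaten validity: no decision rule uses d_IGPP, testing is exploratory, and the arm summaries will be visible. That the signs can conflict is plain arithmetic. The size of the loss depends on assumed normality, correlation and comparator change. With equal SDs it is about 20-30% extra sampling SD if the comparator does not change, 30-50% at 0.44 SD improvement, and 50-100% at 1 SD, before any small-sample correction. A common divisor does not rescue a trial of eight: at ρ = 0.5 its central 95% range still includes zero at the planning effect.

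**What to change.** Amend SAP 9.9 as follows, and carry it to the scales in 9.9.2.

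1. Report the difference in mean CAPS change, full dose minus comparator, with a 95% t interval (6 df at n = 5 and 3).
2. Report one standardised difference: the difference in item 1 divided by s and multiplied by J(12) = 1 - 3/47 = 0.936, where s² = [(nT-1)(vpreT+vpostT) + (nC-1)(vpreC+vpostC)] / [2(nT+nC-2)]. Scale the limits from item 1 by the same factor and label that interval approximate.
3. Keep d_IGPP as a secondary display for comparability with other studies.

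The divisor s uses variances the SAP already computes. It is preferred to a baseline-only SD because protocol 4.2.1 requires a CAPS score of at least 50 at entry. That can narrow the baseline spread, and the baseline-only version loses its advantage when visit-12 spread is larger.

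The cost is SAP wording and a few lines of SAS, with no extra subjects or visits. A wide interval becomes visible: the mean half-width in item 1 is about 1.7 SD at ρ = 0.5 (2.0 at 0.3, 1.3 at 0.7). J(12) leaves the estimate up to 3% too large, because pre and post scores are correlated. In simulation at a true difference of 0.8 SD, the t interval covers 95% and the scaled interval 94-95%; the latter falls to about 93% if the comparator's visit-12 SD is 1.5 times the full-dose arm's.
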